
homeostasis and PCOS. Signatures of systemic disruption of lipid homeostasis, which can manifest itself in serum lipidome, would be useful for early intervention to alleviate the consequences of PCOS. They may also yield clues to identify novel therapeutic targets for PCOS, which currently have no cure.

Hypothesis: Longitudinal evolution of systemic lipidomic signature can reflect onset of PCOS.

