#### **1.2** Hypothesis and aims and objectives (up to one page):

This proposal aims to longitudinally monitor a population of young adult women in nested casecontrol study design to identify changes in serum lipidome that can act as early marker for PCOS onset. Specific aims of the project are as follows:

1)Thorough physio-clinical evaluation including analysis of true adiposity, serum biochemistry, ovarian morphology and liver steatosis and fibrosis.

2)Characterization of differences in serum lipidome of PCOS and naive subjects.

3)Characterization of evolution of lipidomic signature during onset of PCOS in naive subjects.

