#### **1.3** Significance of the project (up to one page):

This project will involve application of modern tools for thorough analysis of patient physiology and status of PCOS. It will also involve application of cutting edge chromatography and mass spectrometry platforms for detailed characterization of lipidome. Success of the project will be of immediate help to clinicians and patients in terms of screening and diagnosis of PCOS. In addition, the results may also yield clues to identify novel therapeutic targets for PCOS.

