(B) GC-MS Analysis: Lipid extract will be mixed with internal standards for derivatization and extraction. Methyl esters of fatty acids will be prepared via esterification using Methanolic HCl. Methyl esters will be extracted using hexane, evaporated to dryness under nitrogen and reconstituted in hexane containing internal standard for GC-MS quality control. For steroids, samples will be derivatized using MSTFA containing 0.5% TMSI. Compounds will be separated on a HP5-MS or DB5 column with helium as the carrier gas in gas chromatograph (Agilent 7890B) and ionized through electron impact ionization and analyzed using a single quad mass spectrometer (Agilent 5977B). Total ion chromatogram will be aligned and deconvoluted to extract features and identify changes in composition. Identification of compounds of interest will be through analysis of fragmentation pattern, matching against NIST Library and comparison with authentic standards (whenever available).

**Data mining:** Data redundancy often leads to model over fitting in multivariate analysis. Such redundancy may arise due to in-source fragmentation and adducts in mass spectrometry. Inter-feature correlation will be examined across samples to identify covariant features. In case, they appear within same retention time window, raw chromatograms will be analyzed to identify putative adducts or fragments. They will be excluded from further analysis. Principal component analysis (PCA) will be used to examine any segregation of lipidomic signature and their correlation with phenotypes of interest (PCOS and sub-features of PCOS). Supervised analysis (PLS-DA and OPLS-DA) will be used to identify features that could predict phenotypes of interest. Iterative 'leave-one-out' cross validation (number of iteration

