> 20% of the size of the nested cohort) will be used to validate the model. For univariate analysis non-parametric statistical test assuming unequal variance will be employed given the limited sample size. Unpaired Mann-Whitney 'U' test with Bonferroni correction for multiple testing will be used identify lipids (say, set 'A') that shows significant difference in abundance between controls and cases at a given time point. Paired Mann-Whitney test with Bonferroni correction will be used to identify lipids (say, set 'B') that shows significant change in abundance with disease onset in naive subjects. Molecules (say, set 'C') that shows similar pattern of change with time in all three groups, i.e., subjects that present PCOS at beginning, those that develop PCOS during the study and those who never develop PCOS, will be excluded from further analysis to identify putative biomarkers. Rest of the molecules that are common in both sets (A and B) and shows similar pattern of change associated with disease status will be tested as potential biomarkers related to PCOS. In addition, the correlation between lipidomic signatures and non-PCOS clinical or biochemical parameters (such as, body weight, BMI, WC, body fat, fasting glucose, insulin concentration, liver fibrosis score, etc) will be examined. Receiver operating characteristic (ROC) analysis will be performed to examine the sensitivity and specificity of these candidate biomarkers for PCOS diagnosis. In case, there are significant number of new cases of PCOS in both 2nd and 3rd year, cases up to 2nd year will be used to identify consensus lipidomic changes associated with PCOS as described above. Rest of the cases will be used to prospectively validate PCOS markers through ROC analysis. In addition, the ability of baseline abundance of such molecules to predict PCOS incidence at a later time point will be examined using ROC analysis. This would help to identify a multivariate signature that could help to predict PCOS risk in naive subjects.

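### The baseline-prediction ROC is run on lipids already selected in the same women, with no multiplicity control and no held-out or cross-validated estimate; Bonferroni covers only the two screens before it

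*Protocol*

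**What the plan says.** The title question is prediction of PCOS onset. The hypothesis (Protocol, Lipid Metabolism and PCOS) is that "Longitudinal evolution of systemic lipidomic signature can reflect onset of PCOS", and the third of three unranked aims in section 1.2 is "Characterization of evolution of lipidomic signature during onset of PCOS in naive subjects".

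The Data mining paragraph (section 1.4, Lipidomic Analysis) sets out a sequence:

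- PCA, then PLS-DA and OPLS-DA, for PCOS and its sub-features, with leave-one-out validation of the supervised model.
- Set A: unpaired Mann-Whitney tests with Bonferroni, for lipids with a "significant difference in abundance between controls and cases at a given time point".
- Set B: "Paired Mann-Whitney test with Bonferroni correction will be used to identify lipids" that change with onset in women who were PCOS-free.
- Set C: lipids that move alike in all three groups are dropped.
- Lipids in both A and B become candidate markers and go to a diagnostic ROC.
- If new cases are numerous enough in both later years (no number given), the later cases are kept to validate the PCOS markers by ROC.
- Finally, "the ability of baseline abundance of such molecules to predict PCOS incidence at a later time point will be examined using ROC analysis". The paragraph adds that this should help to find a multivariate signature of risk.

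**The concern.** Bonferroni is attached to A and B only. Those screens ask whether a lipid differs in established PCOS and whether it changes when PCOS appears. Neither asks whether its level before disease separates women who later convert from those who do not. A lipid can pass both screens and have no baseline value at all, so error control on A and B does not carry over to the baseline ROC.

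Nor is the selection independent of that ROC. Set B compares each converter's onset value with her own earlier value, and the earlier value is then used again in the ROC. No resampling or reserved data are stated for this step, since the conditional validation in later cases is described for PCOS markers.

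At stake is a reported predictor of onset that is a chance finding. Section 1.3 states that "Success of the project will be of immediate help to clinicians and patients in terms of screening and diagnosis of PCOS", and a false lead would also use up the independent cohorts planned after the project.

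**Working it through.** **Inputs.** The Protocol gives 200 subjects (Study population), visits at months 1-3, 13-15 and 25-27 (Work plan), and a cited cross-sectional PCOS frequency of 6-50% (Epidemiology). It gives no alpha, number of lipids, number of converters or target AUC, so there is no figure of the plan to reproduce. Everything below rests on stated assumptions.

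**1. Which null each step tests**

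| Step | Null hypothesis | Error control stated |
|---|---|---|
| Set A | no case-control difference at a visit | Bonferroni |
| Set B | no change at onset in converters | Bonferroni |
| Baseline ROC | baseline level unrelated to later PCOS | none |

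**2. Judging k candidates one by one at 5%.** For independent null lipids the chance of at least one false positive is 1 - 0.95^k: 22.6% for k = 5, 40.1% for k = 10, 64.2% for k = 20. With inter-lipid correlation 0.5 (simulated, 5-30 converters against 150 non-converters) it is about 18-20%, 28-30% and 41-44%.

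**3. Size of a chance AUC.** The null standard error is sqrt((n1 + n0 + 1)/(12 n1 n0)). For 20 converters and 140 others this is sqrt(161/33,600) = 0.069, so nominal significance needs 0.5 + 1.96 x 0.069 = 0.64. In simulation with these numbers, correlation 0.5 and 5-20 lipids, the best AUC had a median of 0.60-0.63 and a 90th percentile of 0.65-0.69, and it reached 0.70 in 2-6% of runs.

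**4. Does the A-and-B filter protect the baseline step?** The whole sequence was simulated with 300 lipids, 30 of them shifting 0.8-1.2 SD at onset, and no baseline difference between converters and non-converters. One set of runs used 40 prevalent cases, 160 naive women, within-woman correlation 0.5 and inter-lipid correlation 0 or 0.5. Chance of at least one nominally significant baseline AUC among the lipids passing both screens:

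| Converters | That set of runs | Second simulation, same lipid and shift assumptions |
|---|---|---|
| 15 | 10-35% | 11-43% |
| 20 | 18-64% | 26-57% |
| 30 | 37-74% | 43-80% |

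A third simulation under other assumed settings, counting only runs in which a candidate survived, gave 4-22%, 6-50% and 20-74%. The low ends are settings where few lipids pass. More converters do not cure the problem, because more lipids then pass. The median best chance AUC after filtering was about 0.58-0.65.

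Selection also leaves a mark. Where few lipids passed, the mean baseline AUC of those selected was 0.45-0.47 rather than 0.50, because converters with a low starting value show the larger rise. Some of the nominally significant AUCs therefore point opposite to the onset change. A rule that required the same direction would bring the rate down.

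**5. When the step does not arise.** Reading the paired test as a signed-rank test, its smallest exact two-sided p with n converters is 2/2^n. With n = 10 this is 0.00195, which meets 0.05/m only if m is 25 or fewer lipids. For m = 100 the limit is 0.0005 and n = 12 is needed (2/2^12 = 0.00049). For m = 300 the limit is 0.000167 and n = 14 is needed (2/2^14 = 0.00012). Below those numbers set B is empty.

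**6. After correction.** Testing each of the k AUCs at 0.05/k brought the simulated chance of any false baseline predictor, in the unfiltered runs of step 2, to about 1-5%.

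**The case against.** **The ROC need not be per lipid.** A reader might infer that each lipid gets its own baseline ROC. The text does not say so and names a multivariate signature as the goal. This stands: the percentages above apply only if candidates are judged singly. A combined score does not escape, however. If it is built from lipids selected in the same women, its apparent AUC is optimistic unless selection is repeated inside the validation. The leave-one-out step is stated for the supervised models, not for this ROC.

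**An onset contrast exists.** A reader might infer that nothing in the plan addresses onset. Set B does so, under Bonferroni, and it matches the stated hypothesis. What is absent is a label saying which analysis decides, and that alone would be missing detail.

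**Large chance AUCs are unlikely.** With 10 converters a best chance AUC near 0.70 is common in simulation, and a reader might take that as the expected result. By step 5, set B is then empty for any panel above 25 lipids. Where candidates can exist, the best chance AUC is more modest.

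**No significance rule is stated, the project is exploratory, and a SAP may exist.** Section 18 calls the project exploratory, and sections 14, 17 and 19 look to independent cohorts. This lowers the stakes. It does not correct a step whose sequence the Protocol itself fixes, stating where Bonferroni applies and attaching none here.

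**Conclusion.** The concern holds for the baseline-prediction step. Bonferroni covers screens A and B only. The baseline ROC then reuses the selected lipids and the converters' own baseline values, with no multiplicity control and no held-out or cross-validated estimate. If candidates are judged one by one at an assumed two-sided 5%, the chance of at least one false baseline predictor is roughly 10-80% for 15-30 converters under the assumed 300 lipids and 0.8-1.2 SD shifts, and lower where few lipids pass. The best AUC seen by chance is then typically 0.58-0.65, which is modest but can be nominally significant. With fewer than about 12-14 converters and 100-300 lipids, no candidates reach the step.

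The documents do not support saying that the ROC is run lipid by lipid, that no onset contrast is specified, or that chance AUCs above 0.70 are to be expected. Given the exploratory status and the later cohorts, this should be changed before lipid data are analysed, but it does not undermine the study as a whole.

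**What to change.** In the Data mining paragraph of section 1.4:

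- Define the prediction analysis as one combined baseline lipid score, in women PCOS-free at baseline, for later PCOS diagnosis.
- Redo lipid selection (including the A and B screens, if they feed the score) and the weights inside each cross-validation fold. Report the cross-validated AUC with a confidence interval.
- Report any single-lipid baseline AUCs with Bonferroni over the candidates, or with a permutation adjustment that shuffles converter status and takes the largest AUC each time. If the permutation is to reflect the selection as well, the screens must be rerun within it.
- Label other prediction results exploratory.

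The cost is analysis work only: no extra women, visits or assays. The price is a stricter bar for single lipids and a less favourable AUC. With 20 converters, 140 others and 20 candidates, Bonferroni raises the AUC needed from 0.64 to 0.5 + 3.02 x 0.069 = 0.71.

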#### 2. Work plan & time schedule:

[figure not shown]
Phase-wise plan of action up to post project activities detailing time schedule milestones may clearly be stated.

Time	Activities/work plan	Percent of total activities
0-6 months	Recruitment of JRF, train the JRF, procure consumables and software for lipidomics, procure consumables for biochemical assays.	5%
12-18 month	Procure consumables etc	
24-30 month	Procure consumables etc	
1-3 month	Recruitment of subjects, clinical evaluation, serum sample collection, biochemical assays and diagnosis	10%
13-15 month	Repeat clinical evaluation, serum sample collection, biochemical assays	10%
25-27 month	Repeat clinical evaluation, serum sample collection, biochemical assays	10%
3-34 month	Lipidomic analysis using mass spectrometry, data analysis	55%
32-36 month	Completion of clinical data analysisand manuscript preparation. Completion of lipidomic data analysis, manuscript submission Completion of the project reports and submission	10%

[figure not shown]
#### **1.5** Preliminary data (up to one page):

We conducted a cross sectional, observational study conducted in Gynecology and Obstetrics OPD and Endocrinology OPD of a tertiary care hospital. Women attending the above-mentioned departments with suggestive symptoms were evaluated and selected as cases after satisfying inclusion and exclusion criteria. It was a one and half year's study conducted between December 2015 and May 2017. There were four groups of patients, non-obese PCOS [NOP] (BMI =/< 23 Kg/m2), overweight or obese PCOS [OP] (BMI > 23 Kg/m2), overweight or obese Non-PCOS[ONP] (control group) and non-obese Non-PCOS [NONP] (control group)].

[figure not shown]

Significance is found only between groups 1 and 4 on post hoc analysis of **IL6** values across groups (p<0.05).Significance is found between groups 1 and 4, groups 2 and 4, groups 1 and 3 on post hoc analysis of **IL8** values across groups (p<0.05).

Significance is found only between groups 1 and 3, groups 1 and 4 on post hoc analysis of IL4 values across groups (p < 0.05. No Significance is found between groups on post hoc analysis of IL10 values across groups .

#### Adipokines:

Significance is found between groups 1 and 4 and groups 2 and 4 on post hoc analysis of MCP1 values across groups (p<0.05).

#### **1.6** Year wise "Activity Landmark" of the Project (1st year/ 2nd year/ 3rd year):

First year: Recruitment of JRF, train the JRF, procure consumables and software for lipiomics, and procure consumables for biochemical assays.

2nd year: Lipidomic analysis using mass spectrometry and data analysis.

3rd year: Completion of clinical data analysis and complete the project reports, manuscript for publication

#### 1.7 Year wise deliverables output (preferably point-wise and quantified):

#### 14. Challenges & constraints:

The exact number of PCOS cases at the beginning of the study may be inadequate. In that case, additional subjects from neighbouring hospitals will be recruited. A validation cohort should also be also included in the study, particularly, in case of cross-sectional analysis. Since this longitudinal study has a nested case-control design, the new cases that are diagnosed at later time points will help to test and validate signatures identified at the beginning. Paired statistical analysis of the time series data would significantly help to weed out spurious associations. This is described in the data mining section below. However, it is desirable to have an independent cohort for validation of the results and we would like to involve other hospitals in study once a set of putative markers are identified through this study. Abundance of different lipid molecules are known differ by orders of magnitude. Particularly, phospholipids are very abundant in serum and may mask other low abundance lipids such as bioactive arachidonic acid metabolites during analysis. In order to address the issue, phospholipids will be depleted by passing samples through commercially available phospholipid-binding resin. Platform to platform variability in analysis is often a challenge in translation. To address the issue, in addition to mass spectrometry-based analysis, lipids will further be analyzed using commercially available kits.

This can help to readily validate putative PCOS biomarkers across multiple centres and translate the results into clinically relevant diagnostic assay. This study also offers the opportunity to monitor these subjects further and evaluate the prognostic potential of lipidomic signatures with respect long-term complications of PCOS.

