#### Approved

Kindly note the following:

- The committee understands that your study does not have any commercial sponsor.
- The study proposes to recruit undergraduate medical students at multiple sites. Students, in this
  setting, constitute a vulnerable population. Obtaining Institutional Ethics Committee approval for each
  participating medical college is mandatory. Further if any first year student is below 18 years of age
  at recruitment, then this should be done only after obtaining parental or legal guardian consent.
- The Committee recommends that an awareness and sensitization program may be done for interested students at each participating site before recruitment.

It is placed on record that the decision regarding your proposal was unanimous and therefore did not require any voting procedure. List of members who attended this meeting is provided on the next page. Members absent have reviewed the same documents and have not sent any note of dissent or objection regarding your proposal.

Additional points, if any, mentioned on Page 2 are also to be noted.

Continued on Page 2

Scanned by CamScanner

Institute of Post Graduate Medical Education & Research [name]. IPGME&R Research Oversight Committee

(Institutional Ethics Committee)

Continued from Page 1

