#### **Study population**

Freshers admitted in MBBS course at IPGME&R and SSKM hospital. We aim to recruit 200 subjects.

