#### Sampling methods

All voluntarily consenting adults will be enrolled and clinically evaluated as per Rotterdam criteria to designate them as

PCOS or non-PCOS cases.

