## **19.** Suggested post project activities viz. application areas/field trials/ working with the Line Departments of the State Government etc.

Signatures identified in this study as candidate biomarkers for PCOS will be tested in independent cohorts in collaboration with other hospitals in West Bengal. Hospitals will be selected both in and outside Kolkata so that robustness of these signatures against changes in habitat, life-style and sample handling can be tested

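### The fallback of adding subjects from neighbouring hospitals when PCOS cases are scarce requires no same-site controls, and the named case-control analyses pool all subjects without a site stratum.

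*Protocol*

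**What the plan says.** The base cohort comes from one college. Under Study population the protocol gives "Freshers admitted in MBBS course at IPGME&R and SSKM hospital. We aim to recruit 200 subjects". Under Sampling methods, "All voluntarily consenting adults will be enrolled and clinically evaluated as per Rotterdam criteria to designate them as" PCOS or non-PCOS, so classification follows enrolment.

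Section 14 then gives the contingency. The trigger is that "The exact number of PCOS cases at the beginning of the study may be inadequate", and the response is "In that case, additional subjects from neighbouring hospitals will be recruited". No number defines a shortage. Nothing is said about controls from the added hospitals, the population to be approached there, or common serum handling.

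For the cross-sectional contrast, the Data mining text says: "Unpaired Mann-Whitney 'U' test with Bonferroni correction for multiple testing will be used identify lipids" (set A) that differ between cases and controls at a given time. A paired test within women who develop PCOS gives set B. Only lipids in both sets go forward as candidate biomarkers, and ROC analysis is applied to these. PCA and PLS-DA/OPLS-DA are run alongside. None of these analyses carries a site term or stratum.

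Two other places bear on the point. The ethics committee letter says: "The study proposes to recruit undergraduate medical students at multiple sites". Section 19 plans later validation at other hospitals so that "robustness of these signatures against changes in habitat, life-style and sample handling can be tested".

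**The concern.** The reason for adding hospitals is a shortage of cases, so the added subjects may well contain a higher proportion of cases than the home cohort. Site and PCOS status would then be associated by design. Any lipid that differs between hospitals because of diet, age mix, collection or storage would differ between pooled cases and pooled controls even if PCOS had no effect on it.

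Bonferroni correction limits chance findings and does not remove a systematic difference. Randomised run order and pooled quality-control samples deal with the assay run, not with where the blood was drawn. Leave-one-out cross-validation cannot expose the problem, because each held-out sample carries the same link between site and status.

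At stake is aim 2, the comparison of the PCOS and naive lipidomes, which rests on this contrast. The protocol itself criticises earlier lipidomic studies for not accounting for confounders such as BMI and age.

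**Working it through.** The protocol gives no power calculation, alpha, effect size or lipid count, so there is no figure of its own to reproduce. What follows is an illustration.

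**Inputs from the protocol**
- Planned enrolment: 200 (Study population).
- PCOS proportion: 6% to 50% (Epidemiology, Table 1 and the text below it). Expected home cases: 200 × 0.06 = 12 up to 200 × 0.50 = 100. The contingency matters at the low end, so take 12 cases and 188 controls.
- Test: unpaired Mann-Whitney U with Bonferroni correction (Data mining).

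**Assumptions**
- 28 added cases, giving 40 in all.
- Normally distributed lipid levels with no PCOS effect, and a constant site shift of 0.25 to 1.0 SD.
- Two-sided 0.05, and 300 lipids for Bonferroni (0.05/300 = 0.000167).

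**Apparent case-control difference for a null lipid, 0.5 SD site shift**

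Difference = shift × (outside fraction among cases − outside fraction among controls).
- 28 outside cases only: 0.5 × (28/40 − 0) = 0.35 SD.
- 28 outside cases plus 28 outside controls: 0.5 × (28/40 − 28/216) = 0.5 × (0.700 − 0.130) = 0.285 SD.
- Whole cohort of 100 at the same 6% (6 cases, 94 controls): 0.5 × (6/18 − 94/282) = 0.5 × (0.333 − 0.333) = 0.

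**Normal approximation at 0.05**
- Cases only: standard error √(1/40 + 1/188) = 0.174; 0.35/0.174 = 2.01; Φ(2.01 − 1.96) ≈ 52%.
- 28 + 28: standard error √(1/40 + 1/216) = 0.172; 0.285/0.172 = 1.66; Φ(1.66 − 1.96) ≈ 38%.

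**Simulation of the planned test, 3,000 runs per setting: false-positive rate per null lipid at 0.05**

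| Site shift (SD) | 28 cases only | 28 + 28, pooled | Whole cohort, pooled | 28 + 28, site-stratified (van Elteren) |
|---|---|---|---|---|
| 0 | 5.0% | 4.5% | 5.2% | 4.9% |
| 0.25 | 15.9% | 13.7% | 4.7% | 4.9% |
| 0.5 | 50.2% | 34.5% | 4.3% | 5.7% |
| 0.8 | 86.5% | 69.5% | 3.3% | 5.0% |
| 1.0 | 96.9% | 88.2% | 3.4% | 4.8% |

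A separate set of 4,000 runs gave 49.2% for cases only at 0.5 SD. The rank test falls slightly below the normal approximation, as expected.

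**At the assumed Bonferroni level (0.017%)**
- Cases only: 2.2% at 0.5 SD and 20.8% at 0.8 SD.
- 28 + 28, pooled: 0.8% and 7.1%.
- If all 300 lipids were null and shifted by 0.5 SD, the cases-only top-up would put about 300 × 0.022 = 6.6 of them in set A, against 300 × 0.000167 = 0.05 nominally.

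**Effect on ROC**

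With the cases-only top-up and a 0.5 SD shift, a null lipid has an expected AUC of 0.7 × Φ(0.5/√2) + 0.3 × 0.5 = 0.7 × 0.638 + 0.15 ≈ 0.60 instead of 0.50. A genuine marker's AUC could be pushed either way.

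**Why both parts of the fix are needed**

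With outside cases only, stratification also keeps the error near 5% (5.4% at 0.5 SD). It does so because outside cases have no local controls and contribute nothing, so the top-up is wasted. With local controls but no stratum, the error is still 34.5%.

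**The case against.** The strongest reply is that the protocol never plans a cases-only top-up. A reader might infer that PCOS women will be brought in from elsewhere and set against home-college controls. The text does not say so: it speaks of subjects, the sampling rule enrols first and classifies afterwards, and the ethics letter describes medical students at several sites. All of this fits screening whole student cohorts elsewhere, which the table shows is harmless. This stands, and the point is therefore conditional. It does not dispose of the point, because whole-cohort screening is a slow cure for a case shortage: at 6%, 28 more cases need about 28/0.06 = 467 more women, over twice the planned 200. Some enrichment is plausible, and nothing in section 14 rules it out.

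A reader might also infer that site-driven lipids end up as the final biomarkers. The documents do not support that either. A candidate must also be in set B, a within-woman change in which a constant site shift cancels. Later-onset cases and an independent cohort are further checks. This protection is real, but it covers the candidate list only. Aim 2 and PLS-DA/OPLS-DA do not pass through the filter, and the diagnostic ROC estimates still use pooled levels. The filter also depends on having enough new-onset cases.

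Section 19 concerns hospitals chosen for later validation, so it does not show that the neighbouring hospitals differ. It shows only that the authors think such differences could affect a signature.

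Finally, an analysis plan not shown here might add a site term, and at the higher Table 1 rates the contingency might never arise. Both are fair. Still, the protocol names a pooled test, and that test as described cannot adjust for site.

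**Conclusion.** The point holds in conditional form. The contingency does not require controls from the added hospitals, and the named case-control analyses ignore site. If the top-up is enriched for cases, the set A comparison, aim 2, the supervised models and the ROC estimates may be confounded by site.

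For an assumed 0.5 SD shift and 28 added cases, the false-positive rate per null lipid at 0.05 is about 49% with outside cases only and about 35% with equal outside cases and controls left unstratified. It is about 5% with same-site controls and stratification. The shift, the top-up size, the 6% case proportion and the lipid count drive these sizes, and of these only the 6% comes from the protocol. The rates describe set A, not the final candidate list. Closing the gap is a cheap improvement; this is not a flaw that invalidates the study.

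**What to change.** In section 14, state that each added site recruits PCOS and non-PCOS women together, under the same eligibility criteria and serum handling as the home college, and that site is recorded for every subject.

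In the Data mining text, replace the pooled unpaired Mann-Whitney test with a site-stratified rank test (van Elteren) whenever more than one site contributes, and account for site in the PLS-DA/OPLS-DA and ROC analyses.

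The cost is a few sentences and one recorded variable. The downside is that some places at added sites go to controls, so case numbers rise more slowly.
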